## 4 Subject Selection Enrollment and Withdrawal

### 4.1 Inclusion Criteria

1. Pregnant women at  $\geq 37$  weeks gestation by reliable dating criteria as determined by the American College of Obstetricians and Gynecologists (i.e. gestational age supported by one of the following: ultrasound prior to 20 weeks of gestation, fetal heart tones auscultated by Doppler for 30+ weeks, or documented serum or urine pregnancy test 36+ weeks ago)

2. Scheduled induction of labor with indication and timing supported by the Family Birth Center induction of labor guideline entitled “Induction of labor: Indications and Timing”
3. Singleton gestation
4. Cephalic presentation
5. Amniotic fluid index greater than or equal to 5 centimeters
6. Formal prenatal ultrasound documenting the absence of placenta previa
7. Bishop score <9 and cervical dilation <3cm
8. The woman is able to give appropriate consent and has undergone an informed consent process.
9. Maternal age  $\geq$  18 years old at the time of consent.

#### **4.2 Exclusion Criteria**

1. New diagnosis requiring immediate hospitalization for monitoring (such as preeclampsia)
2. Vaginal bleeding
3. Active labor
4. Premature rupture of membranes as determined by positive ferning and as supported by pooling of fluid in the vaginal vault.
5. Uterine tachysystole (>5 contractions in 10 minutes)
6. Nonreassuring fetal heart tracing before or after Foley placement
7. Chorioamnionitis or maternal fever
8. Intrauterine fetal demise
9. Contraindication to vaginal delivery, relative or absolute (i.e. transfundal uterine surgery)
10. Abnormal placentation including a low lying placenta
11. Prior cesarean delivery
12. Intrauterine growth restriction (growth <10th percentile by formal ultrasound)
13. Known major fetal anomaly
14. Human immunodeficiency virus, Hepatitis C, or active herpes infection
15. Maternal cardiopulmonary disease requiring cardiac monitoring during labor
16. Pregestational diabetes
17. Rh isoimmunization
18. Non-English speaking

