#### B. Enrollment of inpatient comparison (usual care) participants

1. Women who decline participation in the outpatient intervention study may be approached to participate in a limited way as inpatient comparison control participants.
2. The study coordinator will screen the OB White Board daily in the Family Birth Center to identify patients presenting for induction of labor who may be eligible for the study, but not captured during the weekly screening process. Eligible women will be approached, after discussion with their attending obstetric provider, to participate in the study as inpatient comparison usual care participants.
3. Four inpatient comparison control participants will be enrolled with the same parity and BMI strata for every outpatient intervention patient enrolled (see III. A. 3. c. above).

- (a) Patient education and consent
  - (a) The patients will be educated the proposed research study.
  - (b) If the patient elects participation, she will undergo informed consent at that time by a trained research study

coordinator, Principal Investigator, Co-Principal Investigator, or authorized obstetric provider.

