    - 3. Cervical dilation at the time of cesarean, if known

4. Stage of labor at the time of cesarean

IV. Maternal outcomes

A. Intrapartum complications

1. Intrapartum fever
2. Chorioamnionitis
3. Suspected or confirmed placental abruption
4. Category II or category III fetal heart tracing requiring in utero resuscitation as documented in the electronic record during the cervical ripening phase only

B. Estimated blood loss at delivery

C. Postpartum hemorrhage: yes/no, if pharmacologic or surgical treatments required

D. Infection (endomyometritis, wound infection, or urinary tract infection within 30 days)

E. Readmission within 6 weeks of delivery and reason

F. Length of inpatient hospital stay (in hours from time of admission to noon on the day of discharge)

V. Fetal outcomes

A. Sex

B. Birth weight (grams)

C. Position at delivery (occiput anterior, occiput posterior, occiput transverse, or unknown)

D. APGAR scores at 1 and 5 minutes

E. Umbilical cord blood gas-pH and base excess

F. Disposition after delivery: level I, II, or III. If II or III, reason for admission.

G. Day of life on which discharge occurred

H. Neonatal death within 30 days and reason

VI. Maternal satisfaction data

A. Average scores for each question on the maternal satisfaction survey (see attached)

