### 3.4 Primary Safety Endpoints

The primary safety outcomes are as follows: heavy vaginal bleeding, severe pain (return to hospital overnight for unrelieved pain), mode of delivery, intrapartum complications (as described above), and fetal outcomes (as described above). These will include overall fetal and maternal survival rates. Based on previous studies, we do not anticipate any difference between safety endpoints in the inpatient vs. outpatient groups.

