#### **4.4.2 Data Collection and Follow-up for Withdrawn Subjects**

Data will not be collected from women who electively withdraw from the study. Data will be collected on all women who are randomized to a treatment group. Should patients from the outpatient group cross over to the inpatient group (i.e. if they meet exclusion criteria), analysis will be by intention to treat.

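### The same events serve as exclusion criteria and as compared harms, with no common time for judging eligibility, so harm comparisons can be biased in either direction

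*Combined protocol and SAP*

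**What the plan says.** **Exclusions.** Section 4.2 has one list for all women. It includes vaginal bleeding (item 2), "Nonreassuring fetal heart tracing before or after Foley placement" (item 6) and "Chorioamnionitis or maternal fever" (item 7). No item states a time of assessment, apart from the reference to Foley placement in item 6.

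**Compared harms.** Section 3.3 IV.A lists "Intrapartum fever", chorioamnionitis, suspected or confirmed abruption, and "Category II or category III fetal heart tracing requiring in utero resuscitation as documented in the electronic record during the cervical ripening phase only". Section 3.4 makes these intrapartum complications primary safety outcomes and adds heavy vaginal bleeding. Section 7.3 tests maternal outcomes between groups.

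**Finding controls.** Under 3.1 III.B, some controls are women who declined the outpatient study. For the rest, "The study coordinator will screen the OB White Board daily in the Family Birth Center to identify patients presenting for induction of labor"; they are women whom the weekly screen missed, and they are approached after discussion with their provider. The only limit on consent time is in 4.3, which expects consent before birth.

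**Outpatients who later meet an exclusion.** Section 4.4.2 says: "Should patients from the outpatient group cross over to the inpatient group (i.e. if they meet exclusion criteria), analysis will be by intention to treat". Section 7.4 analyses every woman enrolled in the prospective stage apart from elective withdrawals. Section 1.4, however, takes a woman out of the trial for bleeding suspected to be abruption. It does the same for membrane rupture, labor or abruption found during post-placement monitoring. Section 4.4.1 says that after placement a woman may be taken out for several reasons, among them concerning bleeding, a nonreassuring tracing, and fever or chorioamnionitis.

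**The concern.** Whether a ripening-phase event bars a woman from the study or counts as an outcome depends on when her eligibility is judged. If that time differs between the groups, harm events are filtered differently before any analysis starts.

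Outpatients consent before they arrive, so their eligibility is settled early. A White Board control may be judged later. If she already has a fever or a nonreassuring tracing, 4.2 as written keeps her out, and her event never enters the control rate. For outpatients the filter depends on which sections govern the analysis set.

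The outcomes at stake are those meant to show that outpatient ripening is safe. Adjusting for baseline factors cannot restore women who were never enrolled or whose records were dropped.

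**Working it through.** **1. The plan's own figure.** Section 7.2 gives 80% power for hospital time with 40 and 160 women, SD 8 h and a difference of 4 h. The standard error is 8 × √(1/40 + 1/160) = 1.414 h. Then 4/1.414 − 1.96 = 0.87, which gives power of 80.7% (80.4% with the t distribution). The figure reproduces and is not in dispute. The plan gives no harm rates, so the rest is illustration.

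**2. Can a control be checked after ripening starts?** No section prevents it. Arrivals are at 0730 or 1930 (3.1 IV for outpatients; 3.1 V, as typical, for randomized-stage controls). Assume that prospective controls use the same slots, that the screen runs once a day, and that it finds only women already in the unit. A screen *a* hours after one slot is then 12 + *a* hours after the other. One slot waits at least 12 h, and with equal use of the slots the mean wait is at least 6 h. The planned control stay is 16 h (7.2).

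**3. Share of control events before the check.** Let w be the share of controls found by the White Board and L the lag from arrival to the check. With events spread evenly over 16 h, the share removed is x = w × L/16. The documents give neither w nor L.

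- w = 25%, L = 4 h: x = 6.25%
- w = 50%, L = 4 h: x = 12.5%
- w = 50%, L = 8 h: x = 25%
- w = 50%, L = 12 h: x = 37.5%

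**4. Effect on the comparison.** Let both groups have the same true rate r, and let a share x of one group's event cases leave both numerator and denominator. That group's observed rate is r(1 − x)/(1 − rx). For r = 10% and x = 25% this is 0.075/0.975 = 7.7%.

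- Control events lost, outpatients kept: 10%/7.7% = 1.30, or about 12 of 160 controls instead of 16, against 4 of 40 outpatients.
- Outpatient events lost, controls kept: 7.7%/10% = 0.77.

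Outpatient/control ratio over a range of assumptions (true ratio 1):

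| r | x | control events lost | outpatient events lost |
|---|---|---|---|
| 5% | 10% | 1.11 | 0.90 |
| 5% | 25% | 1.32 | 0.76 |
| 5% | 50% | 1.95 | 0.51 |
| 10% | 10% | 1.10 | 0.91 |
| 10% | 25% | 1.30 | 0.77 |
| 10% | 50% | 1.90 | 0.53 |
| 20% | 10% | 1.09 | 0.92 |
| 20% | 25% | 1.27 | 0.79 |
| 20% | 50% | 1.80 | 0.56 |

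The spurious difference runs from 0.5 to 8.9 percentage points. At x = 6.25% of control events, the ratio is (1 − 0.00625)/(1 − 0.0625) = 1.06 for r = 10% and (1 − 0.0125)/(1 − 0.0625) = 1.05 for r = 20%.

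**5. Against sampling error.** The standard error of the difference is √[r(1 − r)(1/40 + 1/160)], which is 5.3 points at r = 10% and 7.1 at r = 20%. At x = 25% the bias is 2.3 and 4.2 points, about 0.4 and 0.6 of a standard error.

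**The case against.** The protocol can be read as already treating the exclusions as baseline criteria. Section 4.3 calls women who become ineligible before induction screen failures. Section 4.4.1 speaks of conditions found at presentation. Section 6.2 prescribes an arrival assessment for both groups, and 3.1 III.B.2 refers to women presenting for induction. Late assessment of controls is an inference from silence. Decliners can be approached before induction and need not be affected, and a control once enrolled stays in under 7.4. In the randomized stage, 3.1 V.B.3 manages a control's nonreassuring tracing within the study.

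Much of this stands. It shows that loss of control events is possible, not planned, and limited to White Board controls whose event came before the check. It does not settle the matter, because no sentence places a control's eligibility check before the first ripening agent.

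A reader might infer a stronger claim: control harms are removed and outpatient harms kept, so outpatient ripening must look worse than it is. The documents do not support that. Sections 1.4 and 4.4.1 remove, or allow removal of, outpatients after placement, which would reverse the bias. Sections 4.4.2 and 7.4 deal directly with data handling and the analysis set, which favors keeping these women. However, the data-collection sentence in 4.4.2 covers only randomized women, which leaves the prospective stage unclear.

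Two further limits apply. Tachysystole (4.2 item 5) is an exclusion but not a listed outcome, so it is not part of this overlap. The tracing outcome requires in utero resuscitation and so is not identical to item 6.

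**Conclusion.** The concern holds in limited form. The overlap between exclusions and compared harms is in the text, the time of eligibility for White Board controls is not fixed, and the sections on outpatients with later events conflict. Harm comparisons can therefore be biased in either direction, and neither direction can be asserted from the documents.

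The size rests on assumed event rates, removal shares, lags and even timing of events. Even spread over 16 h may overstate early loss of fever cases if fever comes late. It may understate loss for tracings, which count only in the shorter ripening phase. Ratios of 1.30 or 0.77 are illustrations at 10% risk and 25% removal. The mildest case shown for control loss gives 1.05 to 1.06. At 25% removal the bias is below one standard error of the comparison, but it is systematic and avoidable at little cost. The change should be made.

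**What to change.** 1. State in 3.1 III.B.2 and 4.2 that eligibility of usual-care controls is judged from the charted arrival assessment in 6.2, before the first ripening agent. Events after that point count as outcomes and do not bar enrolment. Section 6.2 notes that the amniotic fluid index is not routine in usual care, so say how that criterion is handled when the value is missing.
2. Record the time of screening and of consent relative to the start of ripening for every woman, so that remaining differences can be reported.
3. Reconcile 1.4, 4.2 item 6 and 4.4.1 with 4.4.2 and 7.4. Leaving outpatient management should be kept distinct from leaving the analysis set, and the wording should cover the non-randomized stage. The clinical criteria for dismissal home need not change.

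The cost is a few sentences and two recorded times; most arrival findings are already in the chart. The downside is that the coordinator must approach some women who have already had a complication, at a suitable moment.

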#### **4.3 Subject Recruitment, Enrollment and Screening**

We anticipate a targeted population of 400, which includes 200 mothers and their 200 infants. Data will be collected from these 400 charts after delivery.

We anticipate that 250 women in total will provide informed consent before giving birth to their babies. That is, we estimate that 50 women who are initially consented for the study will become ineligible for inclusion in the trial, for example due to spontaneous onset of labor, prior to induction of labor. These women will be considered screen failures.

## 4.4 Early Withdrawal of Subjects

### 4.4.1 When and How to Withdraw Subjects

A patient may be withdrawn from the study for several reasons.

First, the patient may decide at any time to cease participation in the trial. She will receive all appropriate medical cares without consequence of her participation in the trial. If she is randomized to the outpatient group, for example, but decides to withdraw before Foley placement, her induction of labor will occur in the standard, inpatient fashion. The induction will commence either that evening or the next morning, as staffing, unit flow, maternal status, and fetal status allow. Similarly, if a woman in the intervention group declines participation in the trial after the Foley catheter has been placed, the Foley catheter can be removed with pursuit of standard, inpatient cervical ripening. Alternatively, she can keep it in place and elect pain management options such as an epidural outside the realm of this study (thereby excluding her from the study and committing her to inpatient management).

Second, the patient may become excluded from the trial for several reasons. A pregnant woman may be found to be an eligible participant when she is approached at her clinic visit; however, before her scheduled induction of labor that will occur several days later, she may become excluded for any of the following reasons:

- 1) She develops a new diagnosis (such as preeclampsia) requiring immediate hospitalization for monitoring
- 2) She develops vaginal bleeding that is unexplained and concerning for labor or placental abruption
- 3) She spontaneously labors and is admitted for anticipated delivery
- 4) She undergoes premature (pre-labor) rupture of membranes
- 5) During indicated fetal heart rate monitoring, the tracing becomes non reassuring such that outpatient management is not recommended
- 6) She develops a fever and/or chorioamnionitis
- 7) There is an intrauterine fetal demise
- 8) She develops a contraindication to vaginal delivery, such as new active genital herpetic lesions
- 9) Intrauterine growth restriction is diagnosed

Finally, the pregnant woman may become excluded from study shortly after arrival to the Family Birth Center for initiation of the planned induction of labor. Any of the above-listed reasons (vaginal bleeding, spontaneous labor, premature rupture of membranes, etc) diagnosed at presentation will be reason to exclude the woman from participation. Furthermore, *after* Foley catheter placement, a patient may be excluded from the trial should any of the following occur:

1. She is diagnosed with a condition that requires immediate admission for induction of labor (such as gestational hypertension or preeclampsia)
2. She develops vaginal bleeding more than spotting that is clinically concerning for placental abruption
3. She spontaneously labors
4. She undergoes premature rupture of membranes
5. The post-placement fetal heart tracing is non reassuring such that outpatient management is not recommended
6. She develops a fever and/or chorioamnionitis

#### **4.4.2 Data Collection and Follow-up for Withdrawn Subjects**

Data will not be collected from women who electively withdraw from the study. Data will be collected on all women who are randomized to a treatment group. Should patients from the outpatient group cross over to the inpatient group (i.e. if they meet exclusion criteria), analysis will be by intention to treat.

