## 7.4 Subject Population(s) for Analysis

We will analyze all subjects who were randomized in the randomized control trial design stage of the study, except those who electively withdrew from the trial. We will analyze all subjects enrolled in the prospective stage of the study, who do not electively withdraw.

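### Women who leave the outpatient pathway by choice appear to count as elective withdrawals and drop out of data collection and analysis, while crossovers who meet exclusion criteria are kept

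*Combined protocol and SAP*

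**What the plan says.** Section 4.4.2 (Data Collection and Follow-up for Withdrawn Subjects) holds three rules:

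- For elective withdrawals: "Data will not be collected from women who electively withdraw from the study".
- For the randomized stage: "Data will be collected on all women who are randomized to a treatment group".
- For outpatient women who cross over to inpatient care: "i.e. if they meet exclusion criteria), analysis will be by intention to treat".

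Section 7.4 (Subject Population(s) for Analysis) takes all randomized women "except those who electively withdrew from the trial". For the second stage it says: "We will analyze all subjects enrolled in the prospective stage of the study, who do not electively withdraw".

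Section 4.4.1 describes what leaving by choice looks like, under the reason that the patient decides to stop taking part:

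- If a woman in the outpatient group "decides to withdraw before Foley placement, her induction of labor will occur in the standard, inpatient fashion".
- The second case applies "if a woman in the intervention group declines participation in the trial after the Foley catheter has been placed". The catheter may then be removed and inpatient ripening pursued.
- Alternatively she may keep the catheter and choose pain relief outside the study, such as an epidural, "thereby excluding her from the study and committing her to inpatient management".

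Section 7.3 (Handling of Missing Data) excludes women without a primary outcome. Section 1.4 and the last part of 4.4.1 describe women with certain events after placement as excluded from the trial.

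**The concern.** All three choices in 4.4.1 move a woman from outpatient to inpatient care, and the documents describe no way to make that move by choice and remain in the study. Two women with the same change of setting can therefore be handled in opposite ways. The one who meets an exclusion criterion is analysed in the outpatient group; the one who prefers to stay is removed. Removal depends on behaviour after allocation or enrolment, and that behaviour bears directly on the primary endpoint.

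Under 3.2, an outpatient woman's hospital time is the placement visit plus the time from readmission to delivery. Hours at home do not count. A woman who stays in hospital loses that saving, so she probably has a longer counted time than one who goes home. In the control group, withdrawing does not change the setting, so the mechanism is not symmetric.

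Safety is affected too. Severe pain and mode of delivery are among the primary safety outcomes in 3.4, and 8.2 requires all adverse events during the study to be recorded. A woman who leaves the pathway because of pain is one whose outcomes matter, yet the first rule in 4.4.2 would collect none. The missing-data rule in 7.3 offers no repair, and outcomes never collected cannot be restored by a later sensitivity analysis.

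**Working it through.** **Reading the rules together.**

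| Event in an outpatient woman | Data collected (4.4.2) | Analysed (4.4.2, 7.4) |
|---|---|---|
| Crosses over because she meets exclusion criteria | Yes | Yes, by intention to treat |
| Leaves by choice, randomized stage | Two adjacent sentences conflict | No |
| Leaves by choice, prospective stage | No | No |

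The sentence on collecting data from all randomized women does not reach the prospective stage. Even in the randomized stage, 7.4 still removes those who leave by choice.

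**The plan's own figure.** Inputs from 7.2: 40 and 160 women, SD 8 h, means 16 h and 12 h, two-sided 5% level.

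Standard error = 8 × √(1/40 + 1/160) = 8 × √0.03125 = 1.41 h. Noncentrality = 4/1.41 = 2.83 on 198 degrees of freedom. Power is 80.4% by the noncentral t distribution and 80.7% by the normal approximation. The stated 80% is reproduced.

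**Size of the distortion.** Let f be the fraction of the 40 outpatient women who switch by choice, and d their mean hospital time minus that of the women kept. Dropping them overstates the reduction by f × d. Two assumptions are needed, because the documents give neither a withdrawal rate nor hospital times for switchers: f from 5% to 20%, and switchers who stay as long as controls, so d = 16 − 12 = 4 h. The women kept average 12 h, so the estimate with switchers dropped is 4.0 h throughout.

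| Switchers | f | Difference if kept | Overstatement f × 4 h | In standard errors (÷ 1.41) | Power if dropped, not replaced | Power if all 40 kept |
|---|---|---|---|---|---|---|
| 2 | 5% | 3.8 h | 0.2 h | 0.14 | 78.7% (38 v 160) | 76.2% |
| 4 | 10% | 3.6 h | 0.4 h | 0.28 | 76.9% (36 v 160) | 71.7% |
| 8 | 20% | 3.2 h | 0.8 h | 0.57 | 72.9% (32 v 160) | 61.5% |

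Both power columns use the same t calculation with SD 8 h. The first uses a 4 h difference with fewer women, the second the diluted difference with all 40. Power is higher when switchers are dropped only because a more favourable difference is then being tested.

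**The case against.** The strongest objection is textual. Section 4.4.1 starts from a woman who stops participating, and inpatient care is what follows. No sentence says that choosing inpatient ripening is itself a withdrawal. That stands, so the reading is an inference. It is nevertheless the natural one: every voluntary change of setting described appears under that decision, and the epidural clause says outright that the woman leaves the study.

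A reader might infer that any unplanned return to hospital is treated as withdrawal. The documents do not support this. The instructions in 3.1 (part IV) tell women to come back for severe pain or any worrying symptom, 3.3 records early return and its reason, and 3.4 counts overnight return for unrelieved pain as a safety outcome. Early return is on-study, which narrows the affected group.

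A reader might also take the gaps of 9.6 h and 11.1 h from the earlier trials in 1.1 as the excess stay of switchers. Added to this trial's 12 h, they would put switchers at 21.6-23.1 h, well above the 16 h assumed for the inpatients they are meant to resemble. Nothing in the documents justifies that.

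Three further limits stand. The distortion under the stated assumptions is modest, at most 0.57 standard errors. The power loss holds only if withdrawals are not replaced. Section 4.3 plans 250 consents for 200 mothers and attributes the surplus to ineligibility before induction; it does not say whether withdrawals are replaced. For the randomized stage, the second sentence of 4.4.2 may mean that the data exist.

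**Conclusion.** The concern holds as an inference from 4.4.1, 4.4.2 and 7.4. Followed as written, the plan drops women who leave the outpatient pathway by choice and keeps those who leave it for exclusion criteria. This is a stated rule that can bias the primary comparison, not merely a missing detail.

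Bias in favour of the outpatient group is plausible, but its direction is not certain: women in either group may withdraw, and no document gives switchers' hospital times. With 5-20% switching and control-like stays, the overstatement is 5-20% of the 4 h target. That is worth correcting but would not by itself overturn a clear result. Loss of these women's safety outcomes does not depend on those assumptions. The point should be fixed; confidence is medium.

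**What to change.** In 4.4.2 and 7.4, separate two events:

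1. **Leaving the outpatient pathway.** Continue to abstract admission and delivery times, outcomes and adverse events from the chart where consent allows. Analyse the woman in the group to which she was randomized or in which she was enrolled.
2. **Withdrawing permission to use records.** Keep only what was collected before revocation, which 9.1 already permits.

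Remove the conflict between the first two sentences of 4.4.2. Reconcile the wording in 1.4 and 4.4.1 that calls women excluded after placement with the intention-to-treat rule in 4.4.2 and the population in 7.4, leaving clinical handling as written. Report withdrawals and crossovers by group with reasons.

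The cost is mostly wording. Section 9.3 already plans abstraction from the electronic record, so no visits are added. The consent form may need a small change with IRB review; it is not among the documents, so it may already make this distinction. Chart abstraction cannot supply the satisfaction survey (6.4), and a gap remains for women who revoke permission. The estimated reduction may also be smaller: with all 40 kept, power is 76.2% at 3.8 h and 61.5% at 3.2 h.
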